## **6.0 SUBJECT REGISTRATION**

Patients will be recruited to participate in this clinical trial during the regular clinical visits of co-investigators. Patients will be given a copy of the consent form for this trial and will have ample time to review the study. The study will be reviewed with the patient by an experienced co-investigator in detail. Patients will be provided with a signed copy of the consent form. Following the signature of a consent form the FHCRC Research Subject Registration Form (**Appendix D**) will be completed and sent to the FHCRC Research Coordinator along with a copy of the signed consent form and protocol specific HIPAA form. The original consent form will remain in the patient's chart. Once this form has been received and screening has been completed, the eligibility checklist (**Appendix E**) will be completed by study staff. The eligibility checklist must be signed by the PI or designee prior to the start of treatment with deferasirox. Ineligible patient will be considered a screen failure and will not be enrolled; however, they may be reconsidered for enrollment at a later date. Patients must be consented prior to any screening procedures and

must be re-consented with each subsequent attempt at screening. An eligibility checklist must be completed with each screening attempt.

## 7.0 TREATMENT PLAN

### 7.1 Agent Administration

Deferasirox is available orally and should be administered per the manufacturer's instructions.

### 7.2 Treatment Schema

Deferasirox will be administered orally per the manufacturer's instructions to achieve a ferritin < 100 ng/mL and, since it is approved for chelation and used regularly for this purpose as standard of care, the dosing and schedule will be at the discretion of the treating clinician based on overall iron loading (ferritin, serum iron), renal function, hepatic function, blood counts, and clinical condition / performance status.

### 7.3 Duration of Therapy

#### 1. Screening phase (up to 4 weeks: Day -29 to Day -1)

Screening evaluations will be performed at one or more clinic visits to determine eligibility for the study.

#### Laboratory Assessments

- CBC with differential
- Creatinine and GFR estimation
- Hepatitis Panel

Screening evaluations include laboratory evaluations as well as a bone marrow aspirate or biopsy. CBC with differential and record of transfusional requirements in the preceding 3 months will be obtained during the baseline screening. Testing for hepatotropic viruses will be performed during the screening phase to include: Hep A antibody, Hep B surface antibody, Hep B surface antigen, Hep B core antibody, Hep C antibody, and Hep C PCR. Baseline ophthalmologic and audiometric examinations will be performed during the screening phase. It is recommended that the screening bone marrow aspirate or biopsy be performed once a patient has been found to be otherwise eligible. The results from the screening bone marrow aspirate or biopsy will be used as the baseline for analyses. Baseline will be defined as the last assessment or procedure conducted prior to the initiation of deferasirox (Day 1). Baseline evaluations must be performed within 30 days of start of deferasirox except the baseline bone marrow biopsy which can have occurred within 30 days of the start of deferasirox and for pregnancy testing in women of childbearing potential which must be performed within 7 days of the start of deferasirox.

#### 2. Treatment phase (up to 52 weeks: Day 1 to Week 26)

Patients will receive deferasirox at a starting dose at the discretion of the treating clinician based on baseline serum ferritin levels, renal function, hepatic function, blood counts, and clinical condition / performance status. The target ferritin level is < 100 ng/mL. The primary endpoint of hematologic improvement in the erythroid lineage will be assessed at 6 months. Nonresponders will be offered the option of alternative treatments including clinical trials if available. The maximum duration of therapy on this protocol is one year.

#### 3. Monitoring (From Start of therapy till day 30 following last dose)

Creatinine and GFR will be assessed every 2 weeks during the first month of therapy and monthly thereafter; more frequent monitoring may be required if clinically indicated. Serum transaminases, bilirubin, and alkaline phosphatase will be checked every 2 weeks during the first month of therapy and then monthly thereafter. The number of RBC transfusions and platelet transfusions will be recorded at each visit, and hematologic response data will be collected monthly. Lab studies may be performed by the local oncologist. Safety assessments will be performed at all study visits with ophthalmologic and audiometric examinations performed at baseline and as indicated (at least yearly). A bone marrow aspirate or biopsy will be obtained after 3 months of treatment and 6 months following initiation of deferasirox. Patients will be followed for an additional 30 days after discontinuation of deferasirox to assess for toxicity.

**Table 2 Summary of Study Related Monitoring:**

Test	Minimal Frequency*
------	--------------------

Serum creatinine, GFR ^	Pretreatment (within 30 days) baseline. Every 2 weeks during the first month and then monthly thereafter.
Urine protein/creatinine ratio (spot-check)	Pretreatment (within 30 days) baseline and at 6 months and 12 months
Serum Ferritin	Pretreatment (within 30 days) baseline and then monthly thereafter
Serum transaminases, bilirubin, alkaline phosphatase	Prior to therapy (within 30 days). Every 2 weeks during the first month and then monthly thereafter
CBC with differential	Pretreatment (within 7 days) baseline and monthly thereafter
Bone Marrow Aspirate or Biopsy	Pretreatment (within 30 days) baseline (screening) and at 3 months and 6 months post-initiation
Auditory and ophthalmic testing	Prior to therapy (within 3 months). Annually thereafter.
Hepatotropic viruses: Hep B surface antibody, Hep B surface antigen, Hep C antibody, and HCV PCR	Pretreatment (within 30 days)
Pregnancy test urine or serum	Pretreatment (within 7 days of start of deferasirox) in women of child bearing potential

\*Testing should be performed more frequently if clinically indicated

^Estimated GFR with the MDRD formula

Please see Study Calendar (**Appendix F**) which will be supplied to the patients to assist with follow up and scheduling of necessary testing.

#### 7.4 Duration of Follow-Up

Patients will remain treated on study for a maximum of one year. The primary endpoint of hematologic improvement in the erythroid lineage based upon the modified IWG criteria (**Appendix G**) will be assessed at 6 months. At the end of 6 months patients who do not respond will be offered the option of alternative treatments including enrollment into clinical trials if possible. The goal is for patients to complete at least 6 months of therapy; however, patients may be removed/withdrawn from the study prior to 6 months as detailed in Section 7.7. Patients will be followed for 30 days following last dose of study related therapy. At the end of one year patients may continue to receive deferasirox but not as part of this trial and they will not be followed for outcomes or toxicities.

#### 7.5 Concomitant Medication and Supportive Care Guidelines

Supportive care measures (e.g. antibiotic prophylaxis and treatment, transfusions) should be carried out according to institutional practice guidelines or the preference of the attending physician.

##### 7.5.1 Permitted Concomitant Therapy

1. All study participants will be allowed, as medically justified, access to RBC and platelet transfusions. Concurrent use of an ESA will be allowed if the patient has been on a stable dose for two months prior to screening and continuation of ESA is medically justified. Combination therapy with a TPO-mimetic (such as Eltrombopag or Romiplostim) and/or G-CSF is allowed as long as the patient has been on a stable dose for two months prior to screening. G-CSF will be allowed in the setting of an acute infection if medically justified. Lenalidomide concurrent use is allowed if they have been on a stable dose for at least 3 months of duration. HMA concurrent use is allowed if they have been on a stable dose for at least 6 months.

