Based on preclinical and clinical data, mechanisms underlying the inferior survival in this population point to excess in labile plasma iron (LPI) as the putative mediator(19). This has prompted the use of ICT to modify the negative effect of iron overload in patients with MDS. Although several reports suggest a survival benefit with ICT (27-31), all of them were non-randomized comparisons and were susceptible to a significant selection bias. We know that patients are selected to receive ICT on the basis of an expected survival; otherwise, they would not live long enough to benefit. Therefore, the improved survival in patients treated with ICT could be completely due to a selection bias that is not necessarily overcome by a matched pair

In a multicenter, open-label, single-arm, 3-year phase II trial (US03), the safety and tolerability of deferasirox was evaluated in lower-risk MDS who had received at least 20 units of RBC and had a serum ferritin  $\geq 1,000 \mu\text{g/L}$ (34). Of the 173 patients that underwent ICT with deferasirox, 51 (28%) experienced hematologic improvement, only seven of which received other MDS related therapy. Therefore, ICT appears to improve hematologic parameters in some MDS patients with iron overload. Mean labile plasma iron (LPI) was measured at baseline in 163 patients, among these patients 68 had elevated levels ( $>0.5 \text{ LPI units}$ ). Concentrations of LPI fell within normal limits in all 47 patients who were assessed at week 13 and remained in the normal range through the duration of the trial (Figure 3). Additionally, there was a decline in the median serum ferritin by 23.2% at one year in the patients who completed at least one year of ICT. Therefore, deferasirox was able to reduce the iron burden in iron-overloaded MDS patients.

[figure not shown]

Figure 3: Mean LPI over 12 months in MDS patients with abnormal LPI at baseline.

The annual discontinuation rates of deferasirox were 45%, 43%, and 35% during years 1, 2, and 3 respectively. The safety profile of deferasirox in this setting was reasonable with discontinuation in 43 patients (24.8%) because of adverse events (such as gastrointestinal disturbances) or disease progression and 23 patients (13.2%) because of abnormal laboratory values (such as increased serum creatinine). All 28 deaths that occurred during the study were considered unrelated to deferasirox.

[figure not shown]

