### 4.2 Endpoints

#### 4.2.1 Primary Endpoint

The primary endpoint is the proportion of patients that achieve erythroid hematologic improvement as defined by the modified IWG response criteria at 6 months(39).

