### **5.2 Exclusion Criteria**

1. If the patient is currently receiving ESA (for example, erythropoietin) with plans to continue during study: Less than 2 months duration of ESA therapy prior to starting study drug and no dose escalation within 2 months of start of study drug.
2. If the patient is being treated with GCSF and/or a TPO-mimetic (for example, Eltrombopag or Romiplostim) with plans to continue during the study: Less than 2 months duration of GCSF or the TPO-mimetic treatment prior to starting study drug; or GCSF and/or TPO-mimetic has been added to ESA therapy within 2 months of start of study drug.
3. If patient is being treated with Lenalidomide with plans to continue during the study: Stable dose for less than 3 months prior to start of study drug.
4. If patient is being treated with HMA (for example, Azacitidine or Decitabine) with plans to continue during the study: Stable dose for less than 6 months prior to start of study drug.
5. Currently enrolled in, or discontinued within the last 14 days from a clinical trial involving an investigational product or non-approved use of a drug, or concurrently enrolled in any other type of medical research judged not to be scientifically or medically compatible with this study.
6. Presence of  $\geq 10\%$  blast by morphologic examination of bone marrow aspirate or biopsy
7. Platelets  $\leq 50,000$
8. Microcytosis on screening CBC (MCV  $< 81$  fL)
9. Active GI ulceration or hemorrhage
10. Have a serious preexisting medical conditions that, in the opinion of the investigator would preclude participation in the study (for example a GI disorder causing clinically significant symptoms such as nausea, vomiting, and diarrhea, or malabsorption syndrome) or that would result in a life expectancy of less than 1 year
11. Known hypersensitivity to deferasirox
12. History of non-transfusional hemosiderosis
13. Prior hematopoietic stem cell transplant for the diagnosis of MDS
14. A second primary malignancy that in the judgment of the principal investigator (PI) or designee may affect the interpretation of results
15. Have an active fungal, bacterial, and/or known viral infection including human immunodeficiency virus (HIV) or viral (A, B, or C) hepatitis
16. Currently using aluminum-containing antacid products
17. History of clinically significant auditory or ocular toxicity with ICT

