### 7.5.3 Prohibited Concomitant Therapy

- Any investigational drug other than study medication is NOT permitted during the study.
- The concomitant administration of deferasirox and aluminum-containing antacid preparations has not been formally studied. Although deferasirox has a lower affinity for aluminum than for iron, avoid use of deferasirox with aluminum-containing antacid preparations due to the mechanism of action of deferasirox.

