**15.0 STATISTICAL CONSIDERATIONS**

We estimate the rate of hematologic response to iron chelation with deferasirox to be 0.25 based on previously published studies in patients with MDS and iron overload. The null hypothesis that the true response rate is 0.05 will be tested against a one-sided alternative. The accrual goal is for a total of 25 patients. The null hypothesis will be rejected if 4 or more responses are observed in 25 patients. This design yields a type I error rate of 0.0336 and power of 0.9008 when the true response rate is 0.25. Descriptive statistics will be performed and the planned number of patients is estimated based on the patients we have that would meet eligibility criteria.

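### A dose increase of an ESA, lenalidomide or a hypomethylating agent before month 6 is not addressed, and no analysis rule stops a response that follows it from counting as deferasirox activity

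*Combined protocol and SAP*

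**What the plan says.** **Entry conditions.** Section 7.5.1 permits a concurrent ESA, or a TPO-mimetic and/or G-CSF, after two months on a stable dose before screening. Lenalidomide needs three months. For HMA, "HMA concurrent use is allowed if they have been on a stable dose for at least 6 months". Section 5.2 and the eligibility checklist (Appendix E) state matching exclusions tied to the start of study therapy; for lenalidomide, "Stable dose for less than 3 months prior to start of study drug".

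**On-study restrictions.** Section 7.5.3 states "Any investigational drug other than study medication is NOT permitted during the study" and otherwise names only aluminum-containing antacids. The removal criteria in Section 7.7 do not mention starting or increasing MDS therapy. Sections 7.4 and 12.2 offer non-responders alternative treatment at the end of 6 months.

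**Endpoint and test.** Section 4.2.1: "The primary endpoint is the proportion of patients that achieve erythroid hematologic improvement as defined by the modified IWG response criteria at 6 months". Appendix G defines the erythroid response as a hemoglobin rise of at least 1.5 g/dL, or a reduction of at least 4 RBC transfusions per 8 weeks, lasting at least 8 weeks. Section 15.0: "The null hypothesis that the true response rate is 0.05 will be tested against a one-sided alternative". Planned enrollment is 25, and rejection needs at least 4 responders. Section 7.7 states that the analysis is by intent to treat and that withdrawn patients are not replaced.

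**The concern.** Every explicit stability condition looks backwards from screening or from the start of deferasirox. Take a patient on a stable ESA whose dose is raised at month 2 and whose hemoglobin then rises by 1.5 g/dL for 8 weeks. Under Section 12.1 and Appendix G as written, that patient is a primary-endpoint responder.

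There is no control arm in which such changes would also occur, and four responses decide the trial, so a single misattributed response is a quarter of what is needed. The error runs in one direction, because these agents are given for the same disease and, in several cases, for the same anemia.

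The protocol shows awareness of the issue. When it summarizes the earlier three-year deferasirox trial (US03) in Section 2.2, it notes of the 51 responders that "only seven of which received other MDS related therapy". It makes no such separation for its own endpoint.

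**Working it through.** **Step 1: where a rule could sit.**

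| Place | Content on an on-study change of MDS therapy |
|---|---|
| 5.2, 7.5.1, Appendix E | Stability before entry only; one express on-study allowance, G-CSF for acute infection |
| 7.5.3 | Investigational drugs and aluminum antacids only |
| 7.7 | None |
| 4.2.1, 12.1, 15.0 | None |
| Appendix G | None for response; the footnote about another explanation belongs to progression or relapse after improvement |
| Table 2, Appendix F | Transfusion history is scheduled; no row for doses of concomitant MDS drugs |

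**Step 2: the plan's own figures.** Inputs from Section 15.0: n = 25, reject at 4 or more, null 0.05, alternative 0.25. With X binomial:

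- Type I error = 1 − P(X ≤ 3 | 0.05) = 1 − (0.2774 + 0.3650 + 0.2305 + 0.0930) = 0.0341. The plan states 0.0336.
- Power = 1 − P(X ≤ 3 | 0.25) = 1 − (0.00075 + 0.00627 + 0.02508 + 0.06411) = 0.9038. The plan states 0.9008.

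The small differences do not affect this point. The exact values are used below.

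**Step 3: false-positive probability with affected patients.** Let m patients have a co-therapy started or increased and respond with probability q. The other 25 − m respond at the null 0.05. Then

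P(reject) = Σₐ P(Bin(m, q) = a) × P(Bin(25 − m, 0.05) ≥ 4 − a).

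For m = 2, the tails of Bin(23, 0.05) are P(≥4) = 0.0258, P(≥3) = 0.1052 and P(≥2) = 0.3206, so P(reject) = (1 − q)² × 0.0258 + 2q(1 − q) × 0.1052 + q² × 0.3206:

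- q = 0.10: 0.0209 + 0.0189 + 0.0032 = 0.043
- q = 0.15: 0.0187 + 0.0268 + 0.0072 = 0.053
- q = 0.27: 0.0138 + 0.0415 + 0.0234 = 0.079
- q = 0.50: 0.0065 + 0.0526 + 0.0801 = 0.139

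For m = 4, the tails of Bin(21, 0.05) are P(≥4) = 0.0189, P(≥3) = 0.0849, P(≥2) = 0.2830 and P(≥1) = 0.6594. The same formula gives 0.077 at q = 0.15, 0.150 at q = 0.27 and 0.356 at q = 0.50.

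The 27% and 50% are the Section 2.2 rates for lenalidomide outside del(5q) and for HMA in low-risk MDS. The 10% and 15% are assumed lower values. If q is added on top of the 5% null response, as 1 − 0.95(1 − q), the m = 2 results for 27% and 50% become 0.087 and 0.147, which is the same order.

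**Step 4: effect of the fix.** If the m affected patients count as non-responders, with the denominator of 25 and the cut-off of 4 kept, the probability of rejection is P(Bin(25 − m, p) ≥ 4):

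| m | p = 0.05 | p = 0.25 |
|---|---|---|
| 0 | 0.034 | 0.904 |
| 2 | 0.026 | 0.863 |
| 4 | 0.019 | 0.808 |

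This assumes that changes occur independently of response. If they fall mainly on patients who are not responding, less power is lost.

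**The case against.** **New starts.** A reader might infer that new MDS therapy may be begun freely on study. The documents do not support that. Section 7.5.1 is a conditional permission: an ESA begun after entry cannot have been stable for two months before screening. The single express allowance, G-CSF for acute infection, would be needless if new starts were open. Sections 7.4 and 12.2 place alternative treatment at the end of 6 months. This stands: new starts are restricted by implication. It does not reach dose increases in patients already taking these drugs, and it sets no consequence for the endpoint.

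**The ESA exclusion.** Its wording about escalation within two months of starting study drug could be read as covering the period after Day 1. As an entry criterion it can only be checked at entry, and on the wider reading it would still cover ESA alone and two of the six months.

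**Response rates.** A reader might take 27-50% as the likely response to escalation. They are rates for treatment with the agents. The 27% is transfusion independence, not erythroid improvement, and the 50% is an unspecified response. Patients eligible here still have hemoglobin of 10.0 g/dL or less despite months on a stable dose, and the documents give no rate for escalating them. This stands, and it is why the lower range is shown.

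**How many patients.** Seven of 51 in US03 is a fraction of responders who received other therapy, not of treated patients whose therapy changed on study. It does not inform m.

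**G-CSF for infection.** It bears mainly on the neutrophil endpoint, which is secondary and untested, and a short-lived rise would fail the 8-week requirement. This adds little.

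**Intent to treat.** Counting every patient's outcome is a legitimate approach, and a non-responder rule will discard some genuine deferasirox responses. However, Section 15.0 attributes the response rate to chelation ("We estimate the rate of hematologic response to iron chelation with deferasirox to be 0.25"), and an outcome counted whatever else was changed does not measure that.

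**Conclusion.** The point holds in limited form. On-study dose increases are not addressed, new starts are restricted only by implication, and neither has an analysis rule. Followed as written, the plan credits a resulting erythroid improvement to deferasirox, so the direction of bias is upward.

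The size cannot be established from the documents. With two affected patients, the false-positive probability is 0.043-0.053 for response rates of 10-15% and 0.079-0.139 for 27-50%, against 0.034 with none. Both the number of patients and the rate are assumptions, so these figures illustrate how sensitive a cut-off of 4 is and do not forecast the error. The gap should be closed as a cheap improvement.

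**What to change.** Add to Section 12.1 and Appendix G:

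- A patient whose ESA, lenalidomide, HMA or other lineage-active agent is started or increased before the 6-month assessment is a non-responder for the affected lineage in the primary analysis, unless the 8-week response was complete before the change.
- The patient stays in the denominator of 25.
- The response rate is also reported with those responses counted.

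Record the dose and change dates of these agents at the existing monthly visits. The case report forms (Appendix J) are not in the text available, so this field may already exist.

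This is an analysis rule. It leaves clinical use of these agents to the treating clinician.

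The cost is one paragraph, at most one data field, the loss of some genuine deferasirox responses, and the reduction in power shown in Step 4. The type I error cannot exceed 0.034 under the rule.

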##### 7.5.2 Permitted Concomitant Therapy Requiring Caution or Action

- Concomitant use of UGT inducers decreases deferasirox systemic exposure. Avoid the concomitant use of potent UGT inducers (e.g., rifampicin, phenytoin, phenobarbital, ritonavir) with deferasirox. If you must administer deferasirox with 1 of these agents, consider increasing the initial dose of deferasirox by 50%, and monitor serum ferritin levels and clinical responses for further dose modification. Concomitant use of bile acid sequestrants decreases deferasirox systemic exposure. Avoid the concomitant use of bile acid sequestrants (e.g., cholestyramine, colestevam, colestipol) with deferasirox. If you must administer deferasirox with 1 of these agents, consider increasing the initial dose of deferasirox by 50%, and monitor serum ferritin levels and clinical responses for further dose modification

- Deferasirox may induce CYP3A4 resulting in a decrease in CYP3A4 substrate concentration when these drugs are coadministered. Closely monitor patients for signs of reduced effectiveness when deferasirox is administered with drugs metabolized by CYP3A4 (e.g., alfentanil, aprepitant, budesonide, buspirone, conivaptan, cyclosporine, darifenacin, darunavir, dasatinib, dihydroergotamine, dronedarone, eletriptan, eplerenone, ergotamine, everolimus, felodipine, fentanyl, hormonal contraceptive agents, indinavir, fluticasone, lopinavir, lovastatin, lurasidone, maraviroc, midazolam, nisoldipine, pimozide, quetiapine, quinidine, saquinavir, sildenafil, simvastatin, sirolimus, tacrolimus, tolvaptan, tipranavir, triazolam, ticagrelor, and vardenafil)
- Deferasirox inhibits CYP2C8 resulting in an increase in CYP2C8 substrate (e.g., repaglinide and paclitaxel) concentration when these drugs are coadministered. If deferasirox and repaglinide are used concomitantly, consider decreasing the dose of repaglinide and perform careful monitoring of blood glucose levels. Closely monitor patients for signs of exposure related toxicity when deferasirox is coadministered with other CYP2C8 substrates
- Deferasirox inhibits CYP1A2 resulting in an increase in CYP1A2 substrate (e.g., alosetron, caffeine, duloxetine, melatonin, ramelteon, tacrine, theophylline, tizanidine) concentration when these drugs are coadministered. An increase in theophylline plasma concentrations could lead to clinically significant theophylline induced CNS or other adverse reactions. Avoid the concomitant use of theophylline or other CYP1A2 substrates with a narrow therapeutic index (e.g., tizanidine) with deferasirox. Monitor theophylline concentrations and consider theophylline dose modification if you must coadminister theophylline with deferasirox. Closely monitor patients for signs of exposure related toxicity when deferasirox is coadministered with other drugs metabolized by CYP1A2.

